5.2.1 Eligibility Criteria (Prescreening) Part A

Inclusion Criteria

1. Patients must have histologically confirmed locally advanced (after failure of local therapy) or metastatic lung cancer (any histology, except carcinoid) stage IIIa, IIIb or IV (according to the 7th edition of the AJCC staging manual).
2. Existing formalin fixed paraffin embedded biopsy of the lung cancer with potentially sufficient material for analysis.
3. NSCLC with adenocarcinoma histology must have been previously tested for both EGFR mutations and ALK rearrangements (cf Exclusion point 1 below).
4. Able (physically and financially) to travel to University of Colorado for clinical trial treatment.

Exclusion Criteria

1. Known EGFR mutation and/or ALK rearrangement in NSCLC with adenocarcinoma histology.
2. Patients aged ≤ 18 years of age are not eligible for screening.

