5.2.2 Biomarkers to test

We have developed FGFR1 SISH and ISH and RET FISH biomarkers for ponatinib. Our existing data show that both FGFR1 CNG (≥ 4 copies by SISH) and FGFR1 mRNA expression ($\geq 3+$ by in-situ) predict for cell line sensitivity to ponatinib. These neither overlap completely, nor are completely restricted by squamous or adenocarcinoma histology, or indeed NSCLC histology, suggesting the FGFR1 sensitive population may be expandable beyond CNG alone in squamous cancers which is currently being explored in a number of company sponsored trials of other FGFR inhibitors.

Consequently, we aim to test all lung cancer histologies (except carcinoid) for both of these markers initially (Figure 12). However, because of the proven benefit of treatment paradigms directed against EGFR mutations and ALK rearrangements, adenocarcinomas will only be screened if known not to be positive for either marker. In the event that adequate EGFR/ALK testing has not been completed we will send a letter to the patient and their MD explaining the rationale for this in adenocarcinomas per NCCN and CAP guidelines. However, given the potential for clear overlap with KRAS however, KRAS mutant patients will not be excluded from testing and retrospective KRAS testing will be conducted on all FGFR1+ treated patients of unknown KRAS status.

[figure not shown]

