5.4 Assessing and addressing barriers to accrual within Part A/Part B

GRACE, will not only host the trial website but [name], as CEO of GRACE, has committed to increasing awareness of the novel approach undertaken by the trial through dedicated podcasts and regular updates to GRACE's readers. As interest grows, we will utilize all possible patient support and news media opportunities to increase awareness of this trial.

For those patients who have not yet had EGFR or ALK testing performed, given the known benefit of EGFR TKIs and ALK TKIs in EGFR mutant and ALK positive patients, respectively, we feel it may be unethical in some situations to expend tissue on our study's biomarkers first. Consequently, our prescreening process, tracking the NCCN and CAP guidelines for molecular testing, will include pre-written letters for patients with adenocarcinoma (who are not known to be EGFR mutant or ALK positive and have not received testing for both) to give to their primary oncologists explaining the pros and cons of getting this testing before screening for our trial, we will also mention the pros and cons of testing for EGFR and ALK in histologies other than adenocarcinoma including making reference to existing guidelines. We do not plan to pay for this additional standard-of-care testing within our study, however the letter will offer the services of the CMOCO lab to perform the testing billable to insurance, if required. Some patients may not have sufficient material available for molecular screening. While we cannot realistically budget for re-biopsy procedures within this trial, we believe there is a case to be made selected molecular testing to be considered standard-of-care in some situations. Therefore, if there is insufficient tissue for molecular testing our prescreening process will also include pre-written letters for patients to give to their primary oncologists explaining the pros and cons of rebiopsying to get additional material available for molecular testing in this setting. While this molecular preselection will

prevent us from generating additional data on the degree of overlap of EGFR/ALK and the biomarkers assessed within our study, the potential for overlap of these major biomarkers is being explored within ongoing TMA work within the Colorado SPORE. If significant overlap is subsequently suggested from this work, we would consider altering this prescreening restriction through a trial amendment.

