
5.5 Estimates on numbers needed to screen

Part A: The estimated size of Part A is based on literature and tissue microarray data suggesting the total numbers required to screen in order to identify sufficient marker positive patients to populate each of the different cohorts in Part B. Multiple different histological subtypes of lung cancer exist (Travis et al, 1999). Although proportions of the different histologies may differ between countries and be altering over time, for the purposes of sizing estimates we have assumed, based on literature and internal CU data that 88% of lung cancer is NSCLC and 12% SCLC and that 40% of NSCLC represents adenocarcinoma, 25% squamous carcinoma, 10% large cell and 25% other/not otherwise specified (NOS) (Travis et al, 1999). In the absence of additional data, we have also assumed that the prevalence of any given marker in the large cell/other/NOS category will reflect a population consisting of 2/3rds adenocarcinoma and 1/3rd squamous. All lung cancer histologies (NSCLC and SCLC) other than carcinoid will initially be screened in this trial for FGFR1 related biomarkers, and then RET FISH testing will be conducted in FGFR1 double negative cases with either adenocarcinoma or NOS histology when covered as SOC. However, per NCCN and CAP guidelines adenocarcinoma patients will require prior EGFR and/or ALK testing and patients with either an EGFR mutation or ALK rearrangement will be excluded. If patients of other histologies are known to be either EGFR mutant or ALK+, they too will be excluded. If patients known to be wildtype for several other drivers are also prioritized for screening this potential enrichment effect will be even more marked. However, of note our preclinical data shows the potential for FGFR related biomarkers to overlap with some KRAS mutant cases and consequently preselection of KRAS wildtype cases is not required. As data emerge this trial and other sources emerge on the prevalence of these different abnormalities, more focused screening e.g. by different histological subtypes or smoking status, for specific biomarkers may be adopted.

Based on literature and preliminary SPORE TMA data we have assumed the following:

- FGFR1 SISH will be positive in 16% squamous cancers (100% will also be ISH+ve) and 11% adenocarcinomas (0% will be ISH+ve).
- FGFR1 ISH will be positive in 43% squamous cancers (50% will also be SISH+ve) and 11% adenocarcinomas (0% will be SISH+ve)

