- Based on literature data: FGFR1 SISH will be positive in 6% SCLC (no information available on ISH probability).
- RET will be positive in 2% adenocarcinomas. However, in a pan-negative adenocarcinoma/NOS population this is estimated at 20% based on internal data at CU and these patients will be prioritized internally for RET FISH testing after FGFR1 testing over those who have other markers positive.
- Based on literature data: ALK will be positive in 4% adenocarcinoma (excluded from testing in trial).
- Based on literature data (Western population): EGFR mutations will be positive in 10% adenocarcinoma (excluded from testing in trial)

We assume, for practical purposes, EGFR, ALK, RET and FGFR1 marker positivity will behave as if mutually exclusive.

We assume 85% of marker positive patients will enter treatment cohorts.

We assume 5% of patients will be non-evaluable on treatment.

To populate each cohort with 12 evaluable patients, therefore 15 positive patients need to be identified and 13 treated.

22 (20 evaluable) patient FGFR1 double negative cohort (up to additional 36 across all cohorts, but likely mostly within FGFR1 double negative cohort if altered dosing required)

13 patient FGFR1 SISH+ve and ISH+ve cohort

13 patient FGFR1 SISH+ve and ISH-ve cohort

13 patient FGFR1 SISH-ve and ISH+ve cohort

13 patient RET+ve cohort

This makes a total of 74 patients (inc non-evaluable) on the initial treatment study, with up to 100 if additional cohorts are added.

To populate these cohorts will require 700 patients to be screened for FGFR1 SISH and ISH and 266 by RET FISH.

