10.2 Part A Analysis Plan

The goal of Part A is to determine the prevalence of each biomarker and the overlapping frequency of biomarkers (primary objective), which will guide on-going screening for selecting biomarker positive patients for the clinical trial to be conducted in part B. The association between biomarker positivity and the patient clinical and pathological features will be studied (secondary objective) to guide the selection process. In addition, the effectiveness of prescreening locally and nationally will be estimated (secondary objective). Interim analyses will be conducted after 250 and 500 screened samples, before the final analysis, to inform ongoing screening strategies. We will compare and contrast these with the data available from planned and ongoing analyses of tissue microarrays. With 700 samples, the maximum width (distance from the lower limit to the higher limit) of 95% confidence interval for the prevalence of a biomarker will be 0.075.

Biomarker prevalence and its 95% (exact) confidence interval (CI) among the screening patients and for different histologies will be reported. Overlapping frequency and its 95% CI between biomarkers among the screening patients and for different histologies will also be reported. The association between biomarker positivity and clinical/pathological features will be assessed using chi-square test, or Fisher's exact test if necessary, with the features including histology, age at diagnosis of current lung cancer (using age groupings as a categorical variable where necessary), age at diagnosis of metastatic lung cancer, race, sex, current stage, sites of metastatic disease at diagnosis, smoking status, EGFR, KRAS and ALK status. Biomarker prevalence will be reported for each category of features significantly

associated with biomarker prevalence. We will determine the impact of biomarker results on prognosis generating Kaplan-Maier survival curves for overall survival using log-rank testing to compare the survival distributions between marker positive and negative patients for each biomarker. In addition, we will determine the impact of the biomarker results on sensitivity or resistance to standard chemotherapies and patterns of metastatic spread as we have done before (Camidge et al, 2011; Doebele et al, 2012).

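### Part A tests marker positivity against EGFR and ALK status although known positives are excluded, and the KRAS test ignores histology and has uneven KRAS ascertainment

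*Combined protocol and SAP*

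**What the plan says.** Section 10.2 states that the association between biomarker positivity and clinical or pathological features "will be assessed using chi-square test", or by Fisher's exact test if necessary. The feature list includes "smoking status, EGFR, KRAS and ALK status". The synopsis repeats this. Neither place stratifies by histology or gives a rule for missing molecular status.

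Five other statements bear on these tests.
- Section 5.2.1, inclusion: "NSCLC with adenocarcinoma histology must have been previously tested for both EGFR mutations and ALK rearrangements".
- Section 5.2.1, exclusion: "Known EGFR mutation and/or ALK rearrangement in NSCLC with adenocarcinoma histology". The synopsis has the same exclusion.
- Section 5.5 goes further: "If patients of other histologies are known to be either EGFR mutant or ALK+, they too will be excluded".
- Section 5.4 says the preselection will "prevent us from generating additional data on the degree of overlap of EGFR/ALK and the biomarkers assessed within our study", and leaves that question to tissue microarray (TMA) work.
- Section 5.2.2 keeps KRAS-mutant patients in screening and adds that "retrospective KRAS testing will be conducted on all FGFR1+ treated patients of unknown KRAS status". For everyone else, sections 5.3 and 5.5 provide only for capturing molecular results already on file.

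**The concern.** A test against EGFR or ALK status needs patients at both levels of that variable, and the entry rules remove one level. Sections 5.4 and 10.2 therefore contradict each other.

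KRAS is a different case. Overlap between KRAS and FGFR1 is a question the plan raises itself (sections 3.1 and 5.5) and its reason for not excluding KRAS-mutant tumours. Two features could distort the answer. FGFR1 positivity differs by histology in the plan's own figures, and KRAS is likely to differ too, so an unstratified comparison mixes the two. Completeness of KRAS status also depends on the marker under test, because only treated FGFR1-positive patients have gaps filled. Both could make KRAS and FGFR1 look more mutually exclusive than they are. Section 10.2 intends these associations to guide selection, with interim analyses after 250 and 500 samples.

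**Working it through.** **The plan's own figure.** The only precision figure in section 10.2 is a maximum 95% confidence interval width of 0.075 for a prevalence with 700 samples. The exact interval at 350/700 has width 0.0754, which agrees. No figure is given for the association tests.

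**EGFR and ALK.** Section 5.5 assumes 88% NSCLC, 40% of it adenocarcinoma, with EGFR 10% and ALK 4%.
- Adenocarcinomas per 700 lung cancers: 700 × 0.88 × 0.40 = 246. Removed before screening: 0.14 × 246.4 = 34.5.
- Table 10 sums to 95 internal + 94 external = 189 FGFR1-positive patients, leaving 511 negative.
- The 2×2 table is then 0 of 189 against 0 of 511. Chi-square has zero expected counts and cannot be computed. Fisher's test returns p = 1 with an undefined odds ratio.

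**KRAS, complete data.** Inputs from section 5.5 and Figure 14:
- FGFR1 positivity is 43% in squamous, 11% + 11% = 22% in adenocarcinoma and 6% in SCLC. Large cell/NOS behaves as two-thirds adenocarcinoma and one-third squamous.
- The 22% refers to all adenocarcinomas. With EGFR/ALK positives removed it becomes 0.22/0.86 = 25.6%.
- Rescaled to 700 screened: 374 adenocarcinoma-type (90.3 FGFR1-positive, 283.8 negative) and 326 other (107.5 positive, 218.5 negative). That is 198 positives, close to the 189 in Table 10.

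The documents give no KRAS rate by histology. I assume 22% in adenocarcinoma-type and 3% in other tumours, with no association within histology.
- FGFR1-positive: 0.22 × 90.3 + 0.03 × 107.5 = 23.1 mutant, 174.7 wild-type.
- FGFR1-negative: 0.22 × 283.8 + 0.03 × 218.5 = 69.0 mutant, 433.3 wild-type.
- Crude odds ratio = (23.1 × 433.3)/(174.7 × 69.0) = 0.83.

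Over KRAS rates of 15-30% and 1-5% the range is 0.79-0.89. Using 22% instead of 25.6% lowers each value by 0.03-0.05 (0.79 at the base rates). The true within-histology value is 1 throughout.

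**KRAS, with the fill-in.** The three FGFR1-positive cohorts hold 3 × 13 = 39 treated patients, so the fill-in reaches at most 39/189 = 21% of FGFR1-positive patients and no FGFR1-negative patient. The observed odds ratio equals the complete-data one times (s₁₁ s₀₀)/(s₁₀ s₀₁), where s is the chance that KRAS is known, indexed by FGFR1 and then KRAS status. If s depends on FGFR1 alone, this factor is 1.

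Take earlier KRAS results on file for 80% of adenocarcinoma-type and 10% of other cases.
- Without fill-in: FGFR1-positive 16.2 mutant and 66.8 wild-type; FGFR1-negative 50.6 and 198.3. Odds ratio = (16.2 × 198.3)/(66.8 × 50.6) = 0.95.
- Unknown among FGFR1-positive: 0.2 × 90.3 = 18.1 adenocarcinoma-type and 0.9 × 107.5 = 96.7 other. Filling 20.6% adds 3.7 and 20.0 patients, or 1.4 mutant and 22.3 wild-type.
- With fill-in: (17.6 × 198.3)/(89.0 × 50.6) = 0.78.

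| Earlier KRAS testing (assumed) | Without fill-in | With fill-in |
|---|---|---|
| Unrelated to histology and KRAS | 0.83 | 0.83 |
| 80% adenocarcinoma-type, 10% other | 0.95 | 0.78 |
| 60% adenocarcinoma-type, 30% other | 0.87 | 0.79 |
| 50-80% and 5-10%, both ways of applying the 22% | 0.91-0.97 | 0.70-0.78 |
| Mutants 80% known, wild-type 50% | 0.83 | 0.72 |

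If the treated 39 are split evenly between adenocarcinoma-type and squamous-type (13 + 0 + about 6.5 = 19.5 squamous-type, from Figure 14), the upper end of the fourth row becomes 0.79. I therefore quote about 0.70-0.80.

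In the last row stratification would not suffice. Within histology the factor is (0.841 × 0.5)/(0.603 × 0.8) = 0.87, where 0.841 = 0.8 + 0.2 × 0.206 and 0.603 = 0.5 + 0.5 × 0.206.

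**The case against.** A reader might infer that the KRAS test cannot work at all. The documents do not support that. KRAS mutants stay in, both levels are populated, and ascertainment that depends only on FGFR1 status leaves the odds ratio unchanged. Nor is a distortion to about 0.5 supported: under the 80%/10% assumption an odds ratio of 0.52 needs every FGFR1-positive patient filled in, whereas the plan reaches about a fifth.

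It can also be said that no section states that the retrospective KRAS results enter the section 10.2 test. That is true, so the fill-in bias is conditional on pooling. Sections 5.2.2 and 5.5 add that most internal cases, across most histologies, are already profiled, which weakens the dependence of earlier testing on histology. Whether that panel covers KRAS is not stated, and prior testing of external cases is uncontrolled.

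A reader might further infer that KRAS-mutant patients would be wrongly dropped from screening. The enrichment rule in section 5.5 requires at least 100 patients of a subgroup without a single positive, and an odds ratio of 0.7-0.8 does not trigger it. Extra KRAS testing of FGFR1-positive patients can only uncover more KRAS-mutant positives.

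On EGFR and ALK, section 5.4 discloses the limitation, and an empty column yields no result rather than a misleading one. The eligibility lists exclude only adenocarcinoma positives, so if they govern over section 5.5 a few positives of other histologies could enter. They would probably be too few for a useful test. The contradiction with section 10.2 stands.

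**Conclusion.** The EGFR and ALK tests are not estimable by design and should not be in the analysis plan. This follows from the documents alone, subject to reconciling sections 5.2.1 and 5.5 for non-adenocarcinoma positives.

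The KRAS test is feasible but poorly specified. Omitting histology puts the crude odds ratio at roughly 0.8-0.9 when nothing is happening within histology; this rests on the plan's FGFR1 rates and on assumed KRAS rates. The selective fill-in adds a moderate further shift only if its results are pooled and earlier testing followed histology or KRAS result. These are secondary Part A analyses. The primary prevalence estimates and the Part B response decisions do not depend on them.

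**What to change.** In section 10.2 and the synopsis:
- Delete EGFR and ALK from the association tests and state that they are not estimable by design, with overlap left to the TMA work. Reconcile the exclusion in sections 5.2.1 and 5.5.
- Test KRAS within histology with an exact stratified test.
- State which KRAS results enter the test, and report missing KRAS by marker status.
- Repeat the KRAS test using only results that existed before the FGFR1 result, as a sensitivity analysis. This addresses earlier testing that depended on the KRAS result, which stratification does not.

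The retrospective KRAS results need not be discarded. The cost is wording, a little extra analysis, and lower precision in sparse strata.

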The goal of Part A is to determine the prevalence of each biomarker and the overlapping frequency of biomarkers (primary objective), which will guide on-going screening for selecting biomarker positive patients for the clinical trial to be conducted in part B. The association between biomarker positivity and the patient clinical and pathological features will be studied (secondary objective) to guide the selection process. In addition, the effectiveness of prescreening locally and nationally will be estimated (secondary objective). Interim analyses will be conducted after 250 and 500 screened samples, before the final analysis, to inform ongoing screening strategies. We will compare and contrast these with the data available from planned and ongoing analyses of tissue microarrays. With 700 samples, the maximum width (distance from the lower limit to the higher limit) of 95% confidence interval for the prevalence of a biomarker will be 0.075.

Biomarker prevalence and its 95% (exact) confidence interval (CI) among the screening patients and for different histologies will be reported. Overlapping frequency and its 95% CI between biomarkers among the screening patients and for different

histologies will also be reported. The association between biomarker positivity and clinical/pathological features will be assessed using chi-square test, or Fisher's exact test if necessary, with the features including histology, age at diagnosis of current lung cancer (using age groupings as a categorical variable where necessary), age at diagnosis of metastatic lung cancer, race, sex, current stage, sites of metastatic disease at diagnosis, smoking status, EGFR, KRAS and ALK status. Biomarker prevalence will be reported for each category of features significantly associated with biomarker prevalence. We will determine the impact of biomarker results on prognosis generating Kaplan-Maier survival curves for overall survival using log-rank testing to compare the survival distributions between marker positive and negative patients for each biomarker. In addition, we will determine the impact of the biomarker results on sensitivity or resistance to standard chemotherapies and patterns of metastatic spread as we have done before (Camidge et al, 2011; Doebele et al, 2012).

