10.0 ANALYSIS PLAN AND DATA CAPTURE

10.1 Estimated patient numbers

We aim to screen 700 patients in total in Part A (see Section 5 for details of calculation)

Study requirements, in terms of Part B enrollments: Accruing 13 patients for each 12 that will be evaluable.

22 (20 evaluable) patient FGFR1 double negative cohort (up to additional 36 across all cohorts, but likely mostly within FGFR1 double negative cohort if altered dosing required)

13 patient FGFR1 SISH+ve and ISH+ve cohort

13 patient FGFR1 SISH+ve and ISH-ve cohort

13 patient FGFR1 SISH-ve and ISH+ve cohort

13 patient RET+ve cohort

Estimate 74 patient (inc non-evaluable) on treatment study, up to 100 if additional biomarker cohorts are added to be explored.

Excess marker positive patients identified beyond the initial cohort accrual targets, will be directed towards additional expansion of cohorts (following additional support) if evidence of $ORR \geq 40\%$, other studies or remaining standard therapies as appropriate, while generating a larger natural history database relating to *FGFR1/RET* biology.

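### Part A promises category-level prevalence for non-histology features only where the association is significant, so modest and chance differences would be displayed too large

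*Combined protocol and SAP*

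**What the plan says.** The Part A analysis plan (section 10.2, repeated in the synopsis) contains two reporting commitments.

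- **Unconditional.** "Biomarker prevalence and its 95% (exact) confidence interval (CI) among the screening patients and for different histologies will be reported". Overlap between biomarkers is treated the same way.
- **Conditional.** "The association between biomarker positivity and clinical/pathological features will be assessed using chi-square test", or Fisher's exact test where needed. The features are histology, two age variables, and "race, sex, current stage, sites of metastatic disease at diagnosis, smoking status, EGFR, KRAS and ALK status". The display rule follows in section 10.2, where the sentence begins "Biomarker prevalence will be reported for each category of features significantly". It stands unbroken in the synopsis: "Biomarker prevalence will be reported for each category of features significantly associated with biomarker prevalence".

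The purpose of the association analysis is also stated: "The association between biomarker positivity and the patient clinical and pathological features will be studied (secondary objective) to guide the selection process".

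No significance level, sidedness or multiplicity rule is given for Part A. The only multiplicity statement, in section 10.3, concerns the Part B primary objective. Section 10.3 calls its Fisher p-values descriptive, whereas section 10.2 uses significance as the condition for display.

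**The concern.** When an estimate is shown only after passing a significance test, the shown estimates are on average too far from zero. The effect is strongest where power is low. Real but modest differences appear enlarged when they pass and are absent when they do not, and chance differences appear at a size that looks meaningful.

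This matters because the associations are meant to inform who is screened. Section 5.5 allows more focused screening, by smoking status for example, as data emerge. The footnote to Table 10 repeats this, and section 5.1 foresees enrichment from the characteristics of marker-positive patients. None of these three places gives a numerical criterion, so the displayed category prevalences are a natural input. A later reader also could not tell a feature with no association from one with a wide, inconclusive interval.

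**Working it through.** **1. The plan's own precision figure.** Section 10.1: "We aim to screen 700 patients in total in Part A". Section 10.2 gives the maximum width: "95% confidence interval for the prevalence of a biomarker will be 0.075". The Clopper-Pearson 95% interval is widest at 350/700, with width 0.0754, which rounds to the stated 0.075. (Wald: 2 × 1.96 × √(0.25/700) = 0.0741.) The figure reproduces. It describes the overall prevalence, not the categories of a feature.

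**2. Inputs for the display rule.**
- From the documents: 700 screened; planning prevalences of 6% (SISH+ISH+) and 16% (SISH-ve ISH+) in section 5.5, Figure 14; 266 patients for RET FISH (section 5.5).
- Assumed, because the documents give none: two-sided alpha 0.05, two-category features, a 350/350 split (140/560 as a variant), and the true differences.

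**3. What the filter requires.** With pooled prevalence p and 350 per group, a difference is significant when it exceeds about 1.96 × √(p(1−p) × 2/350).
- p = 6%: 1.96 × √(0.0564 × 0.005714) = 3.5 points.
- p = 6.5% (midpoint of 5% and 8%): 1.96 × √(0.0608 × 0.005714) = 3.7 points.
- p = 16%: 1.96 × √(0.1344 × 0.005714) = 5.4 points.

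At about these pooled rates, a true 3-point difference is not displayed at its true size. It is either missing or shown larger.

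**4. Mean displayed difference.** These values come from simulation of two binomial groups with a pooled two-sided test, and were confirmed by exact enumeration.

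| True prevalences | Split | Chance displayed | True difference (points) | Mean when displayed (points) | Ratio |
|---|---|---|---|---|---|
| 6% v 6% | 350/350 | 5% | 0 | 4.2 (absolute) | – |
| 16% v 16% | 350/350 | 5% | 0 | 6.5 (absolute) | – |
| 5% v 8% | 350/350 | 37% | 3 | 4.9 | 1.63 |
| 4.5% v 7.5% | 350/350 | 39% | 3 | 4.75 | 1.58 |
| 14% v 18% | 350/350 | 30% | 4 | 7.2 | 1.79 |
| 13.5% v 18.5% | 350/350 | 44% | 5 | 7.5 | 1.49 |
| 4% v 8% | 350/350 | 61% | 4 | 5.1 | 1.28 |
| 15% v 20% | 140/560 | 31% | 5 | 9.2 | 1.84 |
| 11% v 21% | 350/350 | 96% | 10 | 10.3 | 1.03 |
| 11% v 21% | 140/560 | 85% | 10 | 11.0 | 1.10 |
| 11% v 43% | 154/546 | 100% | 32 | 32.0 | 1.00 |

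The last split is the planning share of squamous cancer: 700 × 0.88 × 0.25 = 154. Without the filter, the mean absolute difference for the two null rows is 1.4 and 2.2 points, and the mean for 13.5% v 18.5% is 5.0, its true value.

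**5. How many false displays.** Eleven features are listed. Histology is reported anyway. EGFR and ALK positives are largely excluded from Part A, so those categories are nearly empty. That leaves 11 − 3 = 8 features. With three markers (SISH, ISH, RET), 8 × 3 = 24 tests. If all are null and independent, expected false displays = 24 × 0.05 = 1.2, and P(at least one) = 1 − 0.95²⁴ = 0.71. Both figures are upper-end illustrations: the two age variables are correlated, SISH and ISH positivity are expected to overlap in squamous cancers, and RET is tested in only about 266 patients.

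**The case against.** The strongest reply is that the plan is more complete than the sentence suggests, and that little depends on it. Several parts of this stand.

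- A reader might infer that all subgroup prevalence is gated on significance. It is not. Histology, the subgroup behind the sizing assumptions and the RET testing order, is reported with exact intervals regardless.
- A reader might infer that null features will be suppressed. The text does not say so: every listed feature will be tested, and the sentence does not contain the word only. The supportable criticism is that nothing commits the investigators to tabulate a feature that fails the test.
- A reader might count 11 × 3 = 33 tests and 1 − 0.95³³ = 0.82. That includes histology, which is not gated, and EGFR and ALK. Section 5.4 concedes that preselection prevents new data on overlap with those two.
- A reader might infer that the filter formally drives enrichment. The one numerical rule, in section 5.5, drops a subgroup from FGFR1 screening when at least 100 have been screened without a positive. It uses counts, not p-values. The comparison with tissue microarray data is a further partial check.
- The size of the inflation rests on an assumed alpha, split and effect, and it nearly disappears for large differences.

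What does not fall away is the display rule itself. For the non-histology features it remains conditional, with no alpha stated, and the less formal routes to enrichment carry no criterion that would bypass it.

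**Conclusion.** The point holds for the listed features other than histology. As written, category-level prevalence is promised for them only when significant, and what is displayed under that rule is biased upward for modest differences. With two-sided 0.05 and 350/350, the ratio is about 1.5 to 1.8 where the chance of display is below one half and 1.28 in the one case run at 61%. A null feature that passes shows roughly 4 points at 6% prevalence and 6.5 points at 16%. Differences of 10 points or more are displayed at 1.00 to 1.10 times their true size.

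The consequence is limited. Overall prevalence, overlap, histology-specific prevalence, the rule on 100 screened without a positive, and the Part B decisions do not depend on the filter. The documents do not support reading this as a threat to a primary result or as a declared intention to withhold null findings. It is a minor defect in how a secondary objective is reported.

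**What to change.** Replace the sentence in section 10.2 and in the synopsis with:

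*Biomarker prevalence with exact 95% CI will be reported for every category of every listed feature with data, for each marker, regardless of the p-value; association p-values are descriptive and unadjusted.*

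The words *with data* avoid asking for EGFR and ALK categories that eligibility largely empties. Section 5.3 already plans to record these features, so sample size, screening and patient conduct do not change. The cost is a longer table, which makes this a free improvement.
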